Patients will be randomized to one of two groups – trial medication or placebo. Randomization schedule will be generated by the study statistician. Block randomization will be used to ensure temporal balance. Once patients have consented to being included in the study, they will be assigned a sequential study number, which will be passed onto the pharmacy study contact at the appropriate site to assign randomization allocation. They will then dispense encapsulated trial medication based on that allocation.

Blinding

This is designed to be a double blinded, placebo controlled trial in which neither the patient nor the clinical team is aware of the group allocation. The medications will be packaged inside a syringe. The medication will be dispensed to the patient with a label that describes both medications, strengths, and administration schedule. The clinical team will be blinded to the allocation and will only receive the dispensed drug from the pharmacy contact and then bring it to the discharging nurse in the recovery room for inclusion with other discharge material.

Preoperative and perioperative procedures

- Patient will undergo standard preoperative procedures including baseline blood work (CBC, BMP, and LFTs), imaging, and medical clearance as required.
- The procedure itself will be performed per standard practice of the surgeon, including choice of instruments, manner of fragmentation, and postoperative management of patient with regards to follow up appointments, stent placement and removal.

Postoperative procedures

- The study pharmacy will disguise the appropriate drug into an unlabeled generic container and dispense the prescription with appropriate instructions.
- In the recovery room, the patient will fill out a 100mm pain visual analog scale sheet which will be kept in the study drawer in the urology department.
- The patient will then be given a packet of materials for data collection along with the syringe with the blinded medication with full administration instructions and safety leaflet.
- The patient will fill out the data sheets for pain scale, trial, rescue and other medication usage, and adverse events on a daily basis for three days. The patient will also fill out the Ureteric Stent Symptoms Questionnaire (USSQ) on postoperative days 1 and 3.
- Patient will then mail the data sheets to the urology department using a provided stamped-addressed envelope or hand in the data sheets at their postoperative appointment.

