The primary outcome measure will be the pain score given by patients on the 100mm continuous visual analog scale (VAS). The VAS is an easy to use instrument for evaluating pain severity. It provides reproducible results that do not differ with age, gender or cause of pain. It is sensitive to treatment effects and data derived from it can be analyzed with standard parametric statistical techniques. Each day, patients will record their maximum and average pain scores. Surveys to record the pain scores and rescue drug (oxycodone) administration will be handed to the patient on day of surgery as well as emailed out via an external REDCap database. We will combine the results from each study and compare the primary outcome between the two groups (i.e. control group and CBD oil group) in two ways: 1. overall, and 2. on a per day basis. Secondary outcomes

- We will compare the number of use, the cumulative and per day usage of analgesic opioid medication between the two groups.
- Usage of other medications, either self-administered, or prescribed will be compared
- The rate of adverse clinical events defined as the rate of adverse drug reactions, rate of unscheduled phone calls, emergency room visits, hospital admissions, and clinic visits will be compared between the two groups. Collection of adverse events will be done by a combination of patient self-report on data sheets and data gathering from electronic medical record to search for evidence of phone calls, emergency room visits, hospital admissions, clinic visit notes.
- Comparison of ureteral stent symptom questionnaire (USSQ) scores on postoperative days 1 and 3.

Subject Information

Target accrual is the proposed total number of subjects to be included in this study at Mayo Clinic. A "Subject" may include medical records, images, or specimens generated at Mayo Clinic and/or received from external sources.

Target accrual: 90

Subject population (children, adults, groups): Adults treated at Mayo Clinic, Arizona for kidney stones with ureteroscopy.

Inclusion Criteria:

- Patients who are diagnosed with kidney or ureteral stones confirmed on imaging (CT of the abdomen and pelvis) and who elect for definitive treatment via ureteroscopy at two sites within a tertiary care institution
- Age 18-75
- Patients of either gender
- Patients of all ethnic backgrounds
- Capable of giving informed consent
- Capable and willing to fulfill the requirements of the study

Exclusion Criteria:

- History of chronic pain

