Previous work looked at pain scores after ureteroscopy for upper urinary tract calculi.^{10,11} From these, and an ongoing study at the Cleveland Clinic, we estimated the mean Visual Analog Scale (VAS) score in the control group when the rescue medication is used to be 3.5 with a standard deviation of 2.5. We assume patient in the experiment group (CBD oil) will have a lower pain score and the placebo group has at least 40% higher pain score before use of the rescue medication. We assume alpha (Type I error) equals to 0.05, power (1 - Type II error) 0.80 and the standard deviation of the pain score is 2.5 for each group. Using two-sided t-test, the sample size estimations under different scenarios are listed in the table below. At Mayo Clinic Arizona we perform over 700 surgical cases for stone disease each year, so patient accrual should be amenable to completion in 12 months.

Pain score in	Pain score in	Effect size	Required sample	Total sample size
treatment group	placebo group	(difference/SD)	size for each group	
2.0	3.5	0.6	45	90
2.25	3.5	0.5	64	128
2.5	3.5	0.4	100	200
2.75	3.5	0.3	176	352

Data Analysis Plan:

All the study data will be summarized by descriptive statistics. We anticipate the baseline characteristics between study groups will be comparable due to randomization. The point estimate and 95% confidence interval (CI) of the primary and secondary outcomes (pain score and USSQ scores) will be reported and compared by the two-sample t-test. If there is imbalance in the baseline characteristics between groups, we will fit a regression model to adjust for the possible confounding effect. The use of analgesic opioid medication (number of use, cumulative and per day usage) will be reported and compared by the two-sample t-test or Chi-square test. All the adverse events observed during the study period will be reported and summarized by frequency count and percentages.

References

- 3. https://www.cdc.gov/drugoverdose/data/index.html. Accessed December 17, 2019.
- 4. Nickel JC, Medical marijuana for urologic chronic pelvic pain. Can Urol Assoc J 2018;12(6Suppl3).

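### The recovery-room VAS has no stated role in the analysis, and covariate adjustment hangs on an undefined imbalance instead of being prespecified

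*Combined protocol and SAP*

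**What the plan says.** **Analysis.** In the Data Analysis Plan, the pain score and USSQ scores "will be reported and compared by the two-sample t-test". The plan continues: "We anticipate the baseline characteristics between study groups will be comparable due to randomization". The only provision for covariates is the sentence "If there is imbalance in the baseline characteristics between groups, we will fit a regression model to adjust for the possible confounding effect". Imbalance is not defined, the characteristics are not listed, and the plan does not say whether the regression replaces the t-test or accompanies it.

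**Recovery-room score.** Under Postoperative procedures: "In the recovery room, the patient will fill out a 100mm pain visual analog scale sheet". The next step reads: "The patient will then be given a packet of materials for data collection along with the syringe with the blinded medication". Patients then complete data sheets at home for pain and for "trial, rescue and other medication usage, and adverse events on a daily basis for three days".

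**Outcome.** Under Outcome measures: "Each day, patients will record their maximum and average pain scores". These scores are compared overall and by day. Neither that section nor Endpoints mentions the recovery-room reading.

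**Sizing.** The Power Statement uses a two-sided t-test: "We assume alpha (Type I error) equals to 0.05, power (1 - Type II error) 0.80". With means of 2.0 and 3.5 and an SD of 2.5, its table gives 45 per group. Target accrual is 90.

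**The concern.** A pain score on the same instrument as the outcome, taken before the study drug is handed over, is the natural candidate for a baseline covariate. The plan collects it but does not say what it is for.

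The trigger also uses the wrong criterion. Randomisation already deals with systematic confounding. What adjustment adds is precision, and that depends on the correlation between the covariate and the outcome. A strongly prognostic covariate is worth adjusting for even when the arms look balanced; an unrelated one is not worth it even when they differ.

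Two things are at stake. The trial is sized with almost no reserve, so a gain that needs no extra patients is worth having if it exists. And because the plan does not say which result is primary once a regression is fitted, the reported conclusion could rest on a choice that was never fixed in advance.

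**Working it through.** **Inputs from the documents.** Two-sided alpha 0.05; power 0.80; means 2.0 and 3.5; SD 2.5 in each group; 45 per group; 1:1 allocation; total 90. The effect size is d = 1.5/2.5 = 0.6. The Power Statement works in 0–10 units and the outcome is on a 100-mm scale, but d is unchanged if means and SD are both multiplied by 10.

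**Assumed.** r, the within-arm correlation between the recovery-room VAS and later pain, is not given. It is varied from 0 to 0.5.

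**1. The plan's own figure.** A noncentral-t calculation for d = 0.6 gives 44.59, so 45 per group and 90 in total. The table reproduces. At 45 per group the noncentrality is 0.6/√(2/45) = 2.846 on 88 df, and power is 80.4%.

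**2. ANCOVA on the recovery-room VAS, fitted regardless of balance.** Adjustment multiplies the residual variance by (1 − r²). Chance imbalance in the covariate inflates the variance of the treatment estimate by 1 + 1/86 on average. One degree of freedom is spent, leaving 87.

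Noncentrality = 0.6 / √[(1 − r²) × (1 + 1/86) × 2/45]

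Equivalent total N = 90 / [(1 − r²)(1 + 1/86)]

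| r (assumed) | Noncentrality | Power | Change from 80.4% | Equivalent total N |
|---|---|---|---|---|
| 0 | 2.830 | 79.9% | −0.5 | 89 |
| 0.1 | 2.844 | 80.3% | −0.1 | 90 |
| 0.2 | 2.888 | 81.5% | +1.1 | 93 |
| 0.3 | 2.966 | 83.5% | +3.1 | 98 |
| 0.4 | 3.087 | 86.3% | +5.9 | 106 |
| 0.5 | 3.267 | 89.8% | +9.4 | 119 |

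**3. Break-even.** Adjustment starts to pay when (1 − r²)(1 + 1/86) = 1, that is at r = √(1/87) = 0.107, or about 0.11.

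**4. What a trigger does.** The plan sets no rule, so this can only be illustrated. Suppose the regression replaced the t-test only when the recovery-room VAS differed between arms at p < 0.05. In simulation, power is then about 81% at both r = 0.3 and r = 0.5, against 83.5% and 89.8% when the model is always fitted. Such a rule fires in about 5% of trials, so the t-test stands in the rest.

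**5. Why the primary result must be named.** In the same simulations (d = 0.6), the adjusted and unadjusted tests fall on opposite sides of 0.05 in about 7% of trials at r = 0.3 and about 12% at r = 0.5.

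**The case against.** The strongest reply is that nothing here is wrong. The trial is sized on a t-test and analysed with one, the test is valid under randomisation, and estimates with 95% confidence intervals are promised. Preferring ANCOVA is then a matter of efficiency. That stands, and it limits the point to an improvement.

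The benefit may also be small. One reading soon after surgery, set against later daily scores that are affected by rescue oxycodone and discretionary adjunct drugs, may correlate only weakly. At r = 0.1 nothing is gained and at r = 0.2 about one point. The documents give no support for any particular r. This stands too.

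The remedy has preconditions. Postoperative procedures gives the order of handover, but no section states when the first dose is taken, or whether the recovery-room score is a baseline value or part of the primary pain score. The daily wording favours a separate baseline but does not exclude the other reading.

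Four stronger readings are tempting and not supported:

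- *That the score is excluded from the analysis.* It could enter the regression as an unnamed baseline characteristic. It has no stated role, which is a weaker claim.
- *That the trigger loses a known share of the gain.* The share depends on a threshold, a covariate list and a primary result that the plan does not set. If the t-test remains primary, none of the gain is kept; under a liberal rule much of it could be.
- *That the trigger inflates type I error.* Across four assumed rules applied mechanically, at r = 0, 0.3 and 0.5, simulated type I error was 0.037 to 0.050. Nothing suggests the sponsor means to choose between results.
- *That 90 is the wrong sample size.* It reproduces from the stated inputs.

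**Conclusion.** The point holds as an efficiency and prespecification weakness, worth considering but not an error. The recovery-room VAS has no stated role, adjustment depends on an undefined imbalance in unnamed characteristics, and the primary result is not named if a regression is fitted. Observed imbalance is the wrong criterion and may leave much or all of any gain unused; how much cannot be determined from the documents.

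Fitting the adjusted model in every case would change power by between −0.5 point (r = 0) and about +9 points (r = 0.5), with no gain below about r = 0.11. These figures assume normal data, 45 complete patients per arm, a pre-dose recovery-room score, and an r that the documents do not supply. A normal distribution with mean 2.0 and SD 2.5 would put about 21% of values below zero, and sheets returned by patients are unlikely all to be complete. Both affect the t-test and ANCOVA alike, so the figures show the size of the change and are not precise to a tenth of a point.

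**What to change.** 1. State in the protocol that the recovery-room VAS is a baseline value, completed before the first dose, and is not part of the primary outcome.
2. If both hold, prespecify ANCOVA with treatment and recovery-room VAS as the primary model for whichever VAS summary is chosen as primary, fitted regardless of observed balance.
3. Give a simple rule for a missing recovery-room value, for example the mean pooled over both arms.
4. Delete the imbalance trigger and report the unadjusted t-test as a sensitivity analysis.
5. If the score is not pre-dose, or is part of the outcome, keep the t-test as the single primary analysis.

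The cost is analysis-plan wording and one protocol clarification, to be settled before unblinding. No new data are collected and N stays at 90. The downside is one degree of freedom, or about 0.5 point of power if r = 0.

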There is a significant amount of research studying the role of cannabinoids in chronic pain management, however very little research has been done on post-operative pain management with cannabinoids.⁶ Specifically within urology, cannabinoids have been shown to be effective in chronic pelvic pain syndrome/chronic prostatitis and help bladder dysfunction in multiple sclerosis patients.^{7,8} Cannabinoid receptors (CB1 and CB2) are present in the bladder, testis, prostate, and vas deferens.⁹ Endogenous cannabinoids interaction with these receptors is involved in the regulation of smooth muscle contractility.⁹ Alpha-receptor antagonists have been found to decrease ureteral stent discomfort by decreasing smooth muscle contractility in the ureter.¹⁰ Theoretically, agonized cannabinoid receptors, if also present in the ureter, as they are in a significant portion of the urinary tract, could also decrease smooth muscle contractility and decrease stent related discomfort. Preclinical data have shown promise for the use in chronic pain with anti-inflammatory, antinociceptive and in the treatment of addiction⁵. There is a gap in the literature to date regarding the use of CBD oil in post-ureteroscopy pain management, and post-surgery in general, but with increasing criticism on opioid prescribing practice, it is an arena that warrants investigation. Therefore, we propose a novel double blind randomized controlled study to compare pain control and safety with CBD oil and oxycodone (opioid) in the post-operative setting after ureteroscopy for urinary calculi.

Study Design and Methods

Methods: Describe in lay terms, completely detailing the research activities that will be conducted by Mayo Clinic staff under this protocol.

This study is designed as a prospective, placebo-controlled, double blind randomized controlled trial. In a blinded fashion, half of the patients will receive the trial drug and half (the control group) will receive the placebo. Both groups will also receive a script for a rescue medication, a commonly used opioid.

The medicinal products will be packaged, and labeled so as to be unidentifiable by the patient. The patient will receive the trial drug or a placebo. Packaging will consist of a syringe labeled with the dosing and administration schedule for both drugs. Drug safety sheets will be provided as part of the package.

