The study will use data that have been collected under another IRB protocol. Include in the Methods section and enter the IRB number from which the research material will be obtained. *When appropriate, note when subjects have provided consent for future use of their data and/or specimens as described in this protocol.*

Enter one IRB number per line, add more lines as needed

Data	Specimens Data & Specimens	
Data	Specimens Data & Specimens	
Data	Specimens Data & Specimens	

Data Analysis

Power analyses may not be appropriate if this is a feasibility or pilot study, but end-point analysis plans are always appropriate even if only exploratory. Provide all information requested below, or provide justification if not including all of the information.

Endpoints

Primary: The primary outcome measure will be the pain score given by patients on the 100mm continuous visual analog scale (VAS).

Secondary:

- We will compare the number of use, the cumulative and per day usage of analgesic opioid medication between the two groups.
- Usage of other medications, either self-administered, or prescribed will be compared
- The rate of adverse clinical events defined as the rate of adverse drug reactions, rate of unscheduled phone calls, emergency room visits, hospital admissions, and clinic visits will be compared between the two groups. Collection of adverse events will be done by a combination of patient self-report on data sheets and data gathering from electronic medical record to search for evidence of phone calls, emergency room visits, hospital admissions, clinic visit notes.
- Comparison of ureteral stent symptom questionnaire (USSQ) scores on postoperative days 1 and 3.

Power Statement:

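### Adverse clinical event rates are promised as a between-group comparison, but the analysis plan names no comparison method and no counting unit for them

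*Combined protocol and SAP*

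**What the plan says.** Both Outcome measures and the Endpoints list under Data Analysis make adverse clinical events a secondary outcome with five components. Both say that the "rate of unscheduled phone calls, emergency room visits, hospital admissions, and clinic visits will be compared between the two groups", and adverse drug reactions belong to the same sentence. The data come from patients' daily sheets and from a search of the electronic record.

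The Data Analysis Plan treats the outcomes in three ways:

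- **Pain and USSQ:** a point estimate and 95% confidence interval, where the "primary and secondary outcomes (pain score and USSQ scores) will be reported and compared by the two-sample t-test".
- **Opioid use:** number of uses, cumulative use and use per day "will be reported and compared by the two-sample t-test or Chi-square test".
- **Adverse events:** "All the adverse events observed during the study period will be reported and summarized by frequency count and percentages".

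No other section supplies a method for adverse events.

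**The concern.** The endpoint text promises a comparison, while the plan describes a summary. Someone following the Data Analysis Plan literally would produce a table with no between-arm estimate and no measure of its uncertainty. The plan does not even say that the table is split by arm.

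Two details would also be left to the analyst:

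- **Scope.** Calls, visits and admissions are part of the endpoint definition, but the adverse-event sentence does not name them. It is unclear whether that sentence covers all five components.
- **Counting unit.** A patient can call or visit more than once. A count may refer to patients or to events, and the denominator of the percentage is not given. Two analysts could follow the plan and report different rates from the same data.

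What is at stake is how one secondary outcome is reported. Percentages without an interval do not show how little a trial of this size can say about differences in event rates.

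**Working it through.** **1. The texts side by side.** The Data Analysis Plan uses the language of comparison for pain, USSQ and opioid use, and names a test for each. For adverse events it uses only the language of summary. The confidence-interval sentence cannot be stretched to cover them, because its parenthesis limits it to pain and USSQ scores. The gap is therefore in the text.

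**2. The plan's own sample size.** Inputs from the Power Statement: means 2.0 and 3.5 (difference 1.5), SD 2.5, two-sided alpha 0.05, power 0.80.

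- Normal approximation: n = 2 × (1.960 + 0.842)² × 2.5² / 1.5² = 43.6, so 44 per arm.
- Noncentral t: 44.6, so 45 per arm and 90 in total.

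The stated 45 and 90 reproduce, and 90 is the target accrual. The calculation concerns pain only. The documents give no power and no expected rate for adverse events, so every event rate or count below is an assumption.

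**3. What an interval would show at 45 per arm.** Newcombe's method combines the Wilson limits (l, u) of the two proportions:

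lower = (p1 − p2) − √[(p1 − l1)² + (u2 − p2)²]

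upper = (p1 − p2) + √[(u1 − p1)² + (p2 − l2)²]

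For 9 of 45 (20%), the Wilson limits are 0.1090 and 0.3382. With 9 patients in each arm, the half-width is √[(0.2000 − 0.1090)² + (0.3382 − 0.2000)²] = √(0.00828 + 0.01910) = 0.1655.

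| Patients with an event | Difference | 95% interval (points) |
|---|---|---|
| 9 vs 9 (20% vs 20%) | 0 | −16.6 to +16.6 |
| 9 vs 4 (20% vs 9%) | 11 | −3.8 to +25.9 |
| 14 vs 7 (31% vs 16%) | 16 | −2.0 to +32.1 |

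If no patient of 45 has a given reaction, the upper two-sided 95% limit for the true rate is 1 − 0.025^(1/45) = 7.9%.

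**4. Why an estimate suits better than a test.** Take a 10-point difference with 45 per arm. The simple half-width is 1.96 × √[p0(1 − p0)/45 + p1(1 − p1)/45]. Chi-square power is Φ[(0.10 − 1.96 × SE0)/SE1], with SE0 pooled and SE1 unpooled. For 10% vs 20%, SE0 = √(2 × 0.15 × 0.85/45) = 0.0753 and SE1 = √[(0.09 + 0.16)/45] = 0.0745. Power is then Φ(−0.64) = 26%. Fisher power is by full enumeration.

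| Assumed rates | Half-width (points) | Power, chi-square | Power, Fisher |
|---|---|---|---|
| 5% vs 15% | 12.2 | 35% | 23% |
| 10% vs 20% | 14.6 | 26% | 18% |
| 20% vs 30% | 17.8 | 19% | 13% |
| 30% vs 40% | 19.6 | 17% | 12% |

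A significance test alone would tell the reader little at any of these rates. An interval would at least show which differences remain possible.

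**The case against.** The strongest reply is that descriptive safety reporting is acceptable in a 90-patient, three-day trial sized on pain alone. The endpoint list and the analysis plan sit in one Data Analysis section. Read together, they suggest rates set side by side by arm, which is an informal comparison. This largely stands. A reader might infer that the promised comparison will not happen at all; the documents support only that no method for it is specified. What survives is that the protocol made this a secondary outcome to be compared, and the plan gives neither a between-arm estimate nor an explicit split by arm.

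Three other stronger readings also go too far:

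- **A false claim of safety will follow.** No section says that equal safety will be claimed, or that similar percentages will be read as no difference. That would be conjecture about a future report.
- **Safety is a core aim, because the Background says the study will "compare pain control and safety with CBD oil and oxycodone (opioid) in the post-operative setting after ureteroscopy for urinary calculi".** That sentence names a contrast that is not randomised: the arms are CBD oil and placebo, and both receive rescue opioid. The hypothesis and both aims do not mention safety.
- **The plan counts events rather than patients.** Its wording is also ordinary language for patients with a percentage. It is silent on the unit, which is an ambiguity and not a contradiction.

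It is also fair to say that the interval widths follow from 45 per arm and assumed counts. They do not measure the wording gap, and the fix does not narrow them. Finally, use of other medications is likewise promised as a comparison and has no method in the plan, so the gap is not unique to adverse events.

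**Conclusion.** The point holds as a minor inconsistency. A stated secondary outcome with five components has no comparison method, no interval and no counting unit, while pain, USSQ and opioid use each have a named comparison. This rests on the text alone and needs no assumed rate.

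The size of the consequence does rest on assumptions. With 45 per arm and 20% of patients affected in each, the interval for the difference is about plus or minus 17 points. Over assumed control rates of 5% to 30%, a 10-point difference would have a half-width of about 12 to 20 points. These figures show why an interval is worth printing; they do not show that any planned conclusion is wrong. The primary analysis and the sample size are unaffected.

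**What to change.** Amend the adverse-event sentence in the Data Analysis Plan so that it matches Outcome measures and Endpoints:

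- Name all five components and say that results are given by arm.
- For each component, report the number and percentage of patients with at least one event, with patients in the arm as the denominator.
- Report the between-arm risk difference with a 95% confidence interval, for example Newcombe's.
- If a p-value is wanted, use Fisher's exact test and label it exploratory.
- Give event counts as supportive information.

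If only description is intended, rewording the endpoint as descriptive and by arm would also remove the mismatch, though the reader would then have no interval.

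The cost is one amended sentence and a few table columns, with no extra patients or data collection. The downside is that wide intervals make the safety statement more cautious. The change should be made before unblinding.
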